### 10.1.2 Sensitivity Analyses

To assess the robustness of the results from the primary analysis of the primary efficacy endpoint, two sensitivity analyses will be performed (Table 3). For subjects who received non-study RBC within 48 hours post-procedure, any sCr values collected after the transfusion of non-study RBC will be censored (i.e., treated as missing) in the sensitivity analysis with PMM approach.

**Table 3: Overview of Primary and Sensitivity Analysis Methods**

Primary or Sensitivity	Statistical Method	Analysis Population	Handling of Missing Data
Primary Analysis	Miettinen and Nurminen	mITT	Observed cases
Sensitivity Analyses	Logistic Regression	mITT	Multiple Imputation (MI)
	Pattern Mixture Modeling (PMM)	mITT	Multiple Imputation (MI)

While the Logistic regression with MI is under missing at random (MAR) assumption, a second sensitivity analysis is to assess the sensitivity to departure from MAR assumption. Specifically, a Pattern-Mixture Model (PMM) with delta-adjustment of imputations based on missing not at random (MNAR) assumption will be implemented as follows:

- a. Use MCMC to create monotone missingness first. Then obtain standard multiple imputations under MAR assumptions for missing sCr values using monotone regression. The missing data are filled in and 1000 complete data sets are created.
- b. For each sCr value that had been missing because of censoring after having received non-study RBC within 48 hours post-procedure, regardless of treatment group, adjust these values by adding  $\lambda$  to the imputed values, where  $\lambda = 0.1$  mg/dL.
- c. Each of the 1000 complete data sets will then be analyzed separately using the same M&N method as used for the primary analysis.
- d. The estimates obtained from the M&N method of each complete data set are combined for inference purposes.
- e. Repeat step b, c, d, with  $\lambda = 0.2, 0.3, \dots, 0.5$  mg/dL or until the conclusion is reversed from the primary analysis, whichever comes first. The larger the value of  $\lambda$  that is required to reverse the conclusion of the primary analysis, the more robust the conclusion is considered to be.

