#### 4.3 Sample Size Estimation

By assuming the proportion of patients with  $\Delta sCr \geq 0.3 \text{ mg/dL}$  to be 30% in the Control arm and no more than a 50% increase from the Control rate (15%) as the non-inferiority margin, a sample size of  $\geq 292$  patients (146 per arm) will provide approximately  $\geq 80\%$  power to declare non-inferiority at the two-sided 0.05 alpha level, assuming the true treatment difference is zero.

Under the same assumptions, sample sizes of 334 patients (167 per arm) and 392 patients (196 per arm) will provide 85% and 90% power, respectively.

In order to maintain sufficient study power to establish non-inferiority for the primary efficacy endpoint, Cerus plans to transfuse a minimum of 320 subjects and may go up to 400.

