### 10.1 Analyses of Primary Endpoint

#### 10.1.1 Primary Analyses

The primary efficacy endpoint is the proportion of patients with a diagnosis of renal impairment defined as any raised sCr level, occurring after transfusion of a study RBC, of  $\geq 0.3$  mg/dL (or 26.5  $\mu$ mol/L) from the pre-surgery baseline within  $48 \pm 4$  hours of the end of surgery.

The corresponding hypothesis is:

$$H_0: P_{Test} - P_{Control} \geq 50\% \times \hat{P}_{Control}$$

*versus*

$$H_A: P_{Test} - P_{Control} < 50\% \times \hat{P}_{Control},$$

where  $P_{Test}$  and  $P_{Control}$  are the event rates for Test (INTERCEPT) and Control groups, respectively, and  $\hat{P}_{Control}$  is the observed Control rate.

The primary analysis of the primary efficacy endpoint will be based on Miettinen and Nurminen (M&N) method stratified by baseline sCr ( $sCr \geq 1.2 \text{ mg/dL}$  vs.  $< 1.2 \text{ mg/dL}$ ) and cardiac surgery group performed (more at risk for renal complications vs. less at risk) based on the observed cases.

The maximum observed post-baseline sCr value will be used to calculate the increase from baseline. If subjects have no post-baseline sCr within 48 hours post-surgery at all, this subject will be treated as missing the primary endpoint.

The common risk difference in proportions and the Mantel-Haenszel score 95% CI for the treatment difference (Test – Control) will be calculated using the stratified M&N method adjusting for baseline sCr and cardiac surgery group type. The estimate of the common risk difference will be calculated based on the stratum risk differences across all strata (Agresti, 2002; p. 231). Non-inferiority will be claimed if the upper bound of the 2-sided M&N Score 95% CI for the treatment difference (Test – Control) is less than 50% of the observed Control rate. Further, if the upper bound is less than 0, then superiority is achieved.

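### The pattern-mixture analysis shifts imputed creatinine by the same λ in both arms, so surviving to λ = 0.5 mg/dL is weak evidence that the non-inferiority result is robust

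*SAP*

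**What the plan says.** SAP section 10.1.1 claims non-inferiority when the upper 95% bound for Test minus Control "is less than 50% of the observed Control rate".

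Section 10.1.2 (steps under Table 3) then sets out a pattern-mixture analysis for departures from missing at random. Creatinine values after a non-study RBC transfusion are set to missing and multiply imputed.

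- Step b: for those values, "regardless of treatment group, adjust these values by adding" λ, starting at 0.1 mg/dL.
- Step c: each completed data set is "analyzed separately using the same M&N method as used for the primary analysis".
- Step e: λ is raised in steps of 0.1 to 0.5 mg/dL, "or until the conclusion is reversed from the primary analysis, whichever comes first". The larger the λ "that is required to reverse the conclusion of the primary analysis, the more robust the conclusion is considered to be".

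No step lets λ differ by arm. No step says whether the limit is recomputed from the shifted data or kept at its primary-analysis value. Section 2 assumes that non-study RBC use is random with respect to treatment arm.

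**The concern.** A non-inferiority conclusion is threatened when the unseen outcomes are worse in Test than in Control. A tipping-point analysis should create that contrast and increase it until the conclusion fails. A λ common to both arms does not create it when the censored shares are similar: both event rates rise together and the difference stays about where it was. If the limit is half the Control rate in the shifted data, it rises too, and the stress runs in the favourable direction.

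At stake is the inference in step e. Reaching λ = 0.5 without reversal would be reported as robustness, although it would largely follow from how the analysis is built. SAP section 2 itself describes non-study RBC use as a possible source of bias and relies on sensitivity analyses to support the mITT result.

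**Working it through.** **The plan's own figure.** Section 4.3 takes the Control proportion "to be 30% in the Control arm and no more than a 50% increase from the Control rate (15%) as the non-inferiority margin", with "power to declare non-inferiority at the two-sided 0.05 alpha level", "assuming the true treatment difference is zero". Per arm, n = (1.96 + 0.8416)² × 2 × 0.30 × 0.70 / 0.15² = 146.5, so 147 against the stated 146; power at 146 is 79.9%. For 85% and 90% power the same formula gives 168 and 197 per arm against 167 and 196. The planning inputs reproduce.

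**Inputs.** From the SAP: Control rate 30%, limit 50% of the Control rate, event threshold 0.3 mg/dL, λ from 0 to 0.5, and 160 per arm (minimum of 320 transfused, 1:1). Assumed, because the SAP gives no figure: normally distributed creatinine change with SD 0.4 mg/dL, censored share f = 25% per arm, and a Test rate of 34%.

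**Formulas.** For an arm with unshifted rate p, let z be the upper-p normal quantile (0.5244 for 30%, 0.4125 for 34%).
- Rate at λ = (1 − f) × p + f × Φ(λ/SD − z).
- Upper bound = difference + 1.96 × √[P_C(1 − P_C)/160 + P_T(1 − P_T)/160].

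**Worked at λ = 0.5** (λ/SD = 1.25).
- Control: 0.75 × 0.30 + 0.25 × Φ(0.7256) = 0.225 + 0.25 × 0.766 = 0.4165.
- Test: 0.75 × 0.34 + 0.25 × Φ(0.8375) = 0.255 + 0.25 × 0.799 = 0.4547.
- Difference 3.8 points; standard error 5.54 points; upper bound 3.8 + 1.96 × 5.54 = 14.7.
- Recomputed limit 0.4165 / 2 = 20.8; held limit 15.0.

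**Balanced use, common λ (30%/34%, 25% censored in each arm), in percentage points.**

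| λ | Difference | Upper bound | Limit recomputed | Limit held |
|---|---|---|---|---|
| 0 | 4.0 | 14.2 | 15.0 | 15.0 |
| 0.3 | 4.1 | 14.8 | 18.6 | 15.0 |
| 0.5 | 3.8 | 14.7 | 20.8 | 15.0 |

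With the limit recomputed, headroom grows from 15.0 − 14.2 = 0.8 to 20.8 − 14.7 = 6.1 points. With it held, headroom stays below one point and the result never tips, although it was borderline at the start.

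**Unbalanced use, common λ (30%/34%).**

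| Censored, Test v Control | Limit | First λ that loses non-inferiority | Upper bound v limit |
|---|---|---|---|
| 25% v 20% | held | 0.2 | 15.6 v 15.0 |
| 25% v 20% | recomputed | none to 0.5 | 17.0 v 19.7 at λ = 0.5 |
| 35% v 20% | recomputed | 0.2 | 17.6 v 16.9 |
| 40% v 20% | recomputed | 0.1 | 16.4 v 15.9 |

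**Shift in Test only, limit held (30%/34%, 25% censored).** At λ = 0.1 the Test rate is 36.4%, the difference 6.4 and the upper bound 16.7 against 15.0. The result tips at the first step.

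**Simulation with multiple imputation and Rubin's rules** (true rates 30% in both arms, 30% censored, SD 0.3, Wald interval). Proportion of trials meeting the rule:
- common λ, limit recomputed: 0.67 at λ = 0, 0.95 at λ = 0.5;
- common λ, limit held: 0.67, 0.63 and 0.67 at λ = 0, 0.2 and 0.5;
- Test-only λ: 0.66 at λ = 0, 0.02 at λ = 0.5.

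**Range.** With equal censoring and the limit recomputed, headroom at 30%/34% is larger at λ = 0.5 than at λ = 0 for every combination checked of SD 0.3, 0.4 and 0.6 with 10%, 15%, 25% and 40% censored.

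**The case against.** Several points on the other side stand.

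- **The analysis can overturn a positive result.** A reader might infer that it reports robustness whatever the data show. The unbalanced cases above refute that: section 2 only assumes balance and admits that avoiding non-study RBCs has been difficult. With the limit held, 25% v 20% is an imbalance of about one standard error (√[0.25 × 0.75/160 + 0.20 × 0.80/160] = 4.7 points) and is enough to tip a borderline result. With it recomputed, 35% v 20% is about three standard errors (15 / 4.9). What the analysis then tests is unequal non-study RBC use, not a difference between arms in the unseen outcomes.
- **The recomputed limit is a reading, not a statement.** Reusing the primary method in step c points to it, but section 10.1.1 refers to the observed Control rate, and shifted imputed values are not observed. So one cannot say flatly that a larger λ makes non-inferiority easier.
- **The primary claim does not depend on this analysis.** With a truly inferior Test arm (45% v 30%, 30% censored, limit recomputed) the simulated pass rate rises from 0.04 to 0.46 as λ goes from 0 to 0.5. A reader might take that as an inflated trial error rate. It is not: non-inferiority is claimed from the observed-case analysis, and under step e a failed result that flips counts as a non-robust failure, not a success.
- **Other analyses address non-study RBC.** Section 10.1.3 plans IPCW, the SROS, and the SROS extended by number of non-study units. They are exploratory, and none is a missing-not-at-random tipping point.
- **A common upward shift is plausible.** Section 2 says that heavily transfused patients are likelier both to have the event and to receive non-study RBCs. That justifies the common shift as one scenario, but not as the only one.

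**Conclusion.** The concern holds in a limited form. With roughly balanced non-study RBC use, a common λ leaves the difference nearly unchanged. Non-inferiority then becomes easier if the limit is recomputed, or the result barely moves if the limit is held. Either way, survival to λ = 0.5 mg/dL is weak evidence of robustness, contrary to step e, and this is the only planned sensitivity analysis for departure from missing at random.

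The direction follows from the SAP's own rule and its balance assumption. The sizes rest on an assumed SD and censored share, normal changes, one value per subject and unstratified Wald bounds. The SAP uses the maximum creatinine and a stratified M&N interval. An independent calculation with an unstratified M&N bound (SD 0.3, 20% censored, 30% in both arms) agrees: the upper bound moves from 10.0 to 10.8 points while the recomputed limit goes from 15.0 to 20.7.

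**What to change.** Amend section 10.1.2 before unblinding.

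1. Step b: replace the single λ with a grid of λ_Test by λ_Control that includes Test-only shifts (λ_Control = 0). The planned common shift remains as the diagonal of the grid.
2. Steps c to e: state that the non-inferiority limit is held at its primary-analysis value.
3. Include λ = 0 in both arms, analysed with the same stratified M&N rule, as the reference.
4. Step e: report the smallest λ_Test − λ_Control at which non-inferiority is lost, and judge robustness by whether a gap of that size is plausible. Show the censored share by arm beside it.

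Extending λ to values missing for other reasons is optional. The cost is SAP wording and a few lines of code. The downside is that the reported tipping point will look less favourable than under the present text.

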## 2. CLINICAL BACKGROUND

The ReCePI study is based on the premise that renal impairment within 48 hours of complex cardiac surgery is an indicator of inadequate tissue oxygenation and is a prognostic indicator that correlates with day 30 post surgery mortality (Lassnigg 2004, Lassnigg 2008). Renal hypoxia is a major determinant of renal impairment, measured as a change in the subjects' serum creatinine (sCr). Renal hypoxia may be caused by impaired renal blood flow, anemia, or qualitative dysfunction of red blood cells resulting in inadequate renal oxygenation. RBCs transfused to correct anemia are hypothesized to prevent renal hypoxia and impairment both by augmenting blood volume and by providing increased oxygen carrying capacity resulting in improved tissue oxygenation. This study is designed to demonstrate non-inferiority of INTERCEPT RBCs (Test) compared with conventional RBCs (Control) in preventing renal tissue hypoxia, as measured by the change in sCr from baseline prior to surgery to sCr levels within the 48-hour period following the completion of surgery.

It is not possible to evaluate the efficacy of transfused Test and Control RBCs in isolation, as study RBCs are naturally diluted by the patients' own blood during transfusion, as well as by re-transfused cell saver blood (a mixture of autologous and transfused RBCs) collected and transfused during surgery. In addition, the study protocol recognizes that cardiac surgery patients may unpredictably require large numbers of RBC components that exceed the available supply of RBCs prepared in accordance with the study protocol, resulting in the transfusion of non-study conventional RBC components. RBC transfusion under these circumstances is "per protocol", however, every effort has been made to avoid non-study RBC transfusions. Prevention of non-study RBC transfusions has proven a challenge. We assume that the use of non-study RBC will be random with respect to treatment assignment into the Test and Control groups as the manufacture of Test and Control RBC inventories has been balanced.

The use of cell-saver and non-study RBC transfusions is potentially problematic, and both the classical mITT and PP analyses study are subject to potential biases, despite execution of the study in compliance with the protocol.

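### The tipping-point analysis adds the same λ to both arms, so with balanced non-study RBC use it hardly stresses a non-inferiority pass, and a large non-reversing λ does not show robustness

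*SAP*

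**What the plan says.** Section 10.1.2 treats creatinine values obtained after a non-study RBC transfusion as missing, imputes them under MAR (step a), and then shifts them. Step b says: "regardless of treatment group, adjust these values by adding" λ, starting at 0.1 mg/dL. Step c has each completed data set "analyzed separately using the same M&N method as used for the primary analysis", and step d combines the results. Step e raises λ up to 0.5 mg/dL or until the conclusion reverses. It ties strength to the size of the shift: "that is required to reverse the conclusion of the primary analysis, the more robust the conclusion is considered to be".

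Two other passages determine how this behaves. In Section 10.1.1 non-inferiority is claimed if the upper 95% bound "is less than 50% of the observed Control rate", so the limit is relative and moves with the Control rate. Section 2 says: "We assume that the use of non-study RBC will be random with respect to treatment assignment into the Test and Control groups".

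Steps c to e do not say whether the limit is recalculated in each λ-shifted data set or held at its value in the primary analysis.

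**The concern.** A tipping-point analysis supports a non-inferiority claim by making the unseen Test outcomes progressively worse relative to Control until the claim fails. A shift common to both arms does not do this. When similar shares of each arm are censored, λ creates similar numbers of extra events on both sides and the difference stays almost where it was. If the limit is also recalculated, it grows with λ because the Control rate grows, and the stress then moves the result towards non-inferiority.

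At stake is how the result is read. Of the two sensitivity analyses in Table 3, this is the only one meant to depart from MAR, and Section 12 gives that as the reason for adding it. Under step e, a pass that survives to 0.5 mg/dL would be presented as robust, although λ put little or no pressure on it.

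**Working it through.** **Inputs from the SAP.** Control rate 30%, with "no more than a 50% increase from the Control rate (15%) as the non-inferiority margin", two-sided 0.05 and true difference zero (Section 4.3); 1:1 allocation (Section 4.2); at least 320 transfused, so 160 per arm (Section 4.3); the relative limit (Section 10.1.1); λ of 0 (added here) to 0.5 in both arms (Section 10.1.2).

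**Assumptions, because the SAP gives no figures.** Share of each arm with a censored value 10-40%. Creatinine change normal with SD 0.286 or 0.4 mg/dL (0.25 and 0.6 also tried). Bounds are unstratified Miettinen-Nurminen on expected rates, without imputation variance.

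**Reproducing the plan's figure.** n per arm = (1.960 + 0.842)² × 2 × 0.30 × 0.70 / 0.15² = 146.5, against 146 stated. Power at 146, 167 and 196 per arm is 79.9%, 84.9% and 90.0%. The planning figures reproduce.

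**Effect of λ on an arm's rate.** With unshifted rate p, censored share f and spread SD, the shifted rate is (1 − f)·p + f·Φ(Φ⁻¹(p) + λ/SD). For p = 0.30, f = 0.30, SD = 0.4 and λ = 0.5: Φ(−0.524 + 1.25) = 0.766, so the rate is 0.7 × 0.30 + 0.3 × 0.766 = 0.440 and a recalculated limit is 0.220.

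**Common λ, balanced censoring, limit recalculated.**

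| Test vs Control | Censored, SD | λ | Upper bound | Limit | Result |
|---|---|---|---|---|---|
| 30% vs 30% | 30%, 0.4 | 0 | 0.100 | 0.150 | pass |
| 30% vs 30% | 30%, 0.4 | 0.5 | 0.108 | 0.220 | pass |
| 30% vs 30% | 25%, 0.286 | 0.5 | 0.109 | 0.224 | pass |
| 36% vs 30% | 30%, 0.4 | 0 | 0.162 | 0.150 | fail |
| 36% vs 30% | 30%, 0.4 | 0.2 | 0.167 | 0.179 | pass |
| 36% vs 30% | 25%, 0.286 | 0.2 | 0.167 | 0.184 | pass |
| 40% vs 30% | 25%, 0.286 | 0.4 | 0.199 | 0.214 | pass (fails at λ = 0) |

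At equal rates (30% censored, SD 0.4) the slack grows from 0.150 − 0.100 = 0.050 to 0.220 − 0.108 = 0.112. In the 36% vs 30% case the difference stays between 0.056 and 0.062 for every λ, so the change to a pass comes from the limit. With 10% censored and SD 0.4 that near miss passes from λ = 0.3, by only 0.0001. For SD 0.25 to 0.6 the switch falls between λ = 0.1 and 0.5.

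**Simulation** (1,500 trials per scenario, 30% censored in each arm, 40 imputations, Rubin's rules, Wald interval, limit recalculated). From λ = 0 to 0.5 the share passing rises from 67% to 91% at true rates of 30%/30%, and from 3% to 26% at 45.5%/30%. At most about 1% of passes tip to a fail.

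**Limit held fixed, λ still common.** The 36% and 40% near misses stay failed at every λ. At equal rates the expected bound (0.108 at most) never reaches 0.150. In simulation about 13-15% of passes tip, and the overall chance of non-inferiority is flat, at 66-70% for every λ (25% censored, SD 0.286).

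**Unbalanced censoring, common λ, limit recalculated.** With 30% of Test and 20% of Control censored, equal rates and SD 0.286, the bound at λ = 0.5 is 0.167 against 0.209, so there is no tip; against a fixed 0.150 the same bound would fail. With 50% and 30% censored and 33% vs 30% (SD 0.4), the pass does tip, at λ = 0.3 (0.196 vs 0.193).

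**λ in Test only, limit fixed at 0.150, 30% vs 30%, SD 0.4.** With 30% censored the bound is 0.100, 0.129 and 0.159 at λ = 0, 0.1 and 0.2, so it tips at 0.2. With 20% censored it tips at 0.3. With 10% it does not tip by 0.5 (0.148).

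**The case against.** The best defence is that a common λ is a coherent scenario. Non-study RBCs are conventional in either arm (Section 5.3.2), and Section 2 says that heavily transfused patients are likelier both to receive them and to have events, without reference to arm. Non-study use is also examined by IPCW, the PPS, the SROS and the stepwise SROS extensions (Section 10.1.3). This stands in part: the scenario is legitimate to report. It still does not probe the departure that threatens a non-inferiority pass, and the other analyses are exploratory and are not tipping analyses.

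The rising limit is inferred. Steps c and d speak of the method and the pooled estimates, and a rate built from shifted imputations is not plainly an observed Control rate. This stands: with a fixed limit the passes created by λ largely disappear. The near-immobility of the difference under balance remains, and so does the silence on which limit applies.

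A reader might infer that the analysis can never overturn a pass. The documents do not support that. Balance is an assumption in Section 2, not a result; clearly heavier censoring in Test can tip a pass, and chance occasionally does. Discarding observed values can also reverse a pass before any λ is added: in one simulation at equal true rates (25% censored, SD 0.286), 16% of primary passes reversed at λ = 0, 11% at 0.1 and 1% at 0.5. Those reversals become rarer as λ grows, which is the opposite of what step e presumes.

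A reader might also infer that a failed trial could be turned into a success. It could not: Sections 10 and 10.1.1 rest the claim on the observed-case mITT analysis, and Section 10.1.2 limits this analysis to robustness. Nor is the rise from 3% to 26% a false-positive rate. Adding λ changes the rates themselves: 45% vs 30% becomes 57.4% vs 44.7% at λ = 0.5 (25% censored, SD 0.286), a difference of 12.7 points, inside a recalculated limit of 22.4.

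**Conclusion.** The point holds in a limited form. Under the SAP's own balance assumption, a λ common to both arms leaves the Test-minus-Control difference almost unchanged. If the limit is recalculated, the analysis drifts towards non-inferiority, and a near miss such as 36% versus 30% can appear as a pass in this sensitivity result. λ is then very unlikely to overturn a pass unless clearly more Test than Control values are censored, so step e's reading of a large non-reversing λ as robustness is not valid for a non-inferiority pass.

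The size depends on the censored share and the creatinine spread, neither of which the SAP gives; the λ at which the near miss becomes a pass ranges from 0.1 to 0.5 over the values tried. The direction under balance and a recalculated limit was the same throughout. This should be fixed, but it concerns a supportive analysis and leaves the primary decision rule untouched.

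**What to change.** Amend steps b to e of Section 10.1.2 before unblinding:

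- **Step b:** let λ differ by arm, either in Test only or as a two-way grid of λ-Test by λ-Control that includes λ-Control = 0. The common-λ scenario can stay as the diagonal of that grid.
- **Start at λ = 0:** report the MAR result from step a first, so that the effect of discarding observed post-switch values is separated from the effect of λ.
- **Steps c and d:** compare every pooled upper bound with one stated limit, 50% of the Control rate observed in the primary analysis.
- **Step e:** define reversal as loss of a non-inferiority conclusion and report the smallest Test-minus-Control shift that causes it. Do not use λ to search for a pass when the primary analysis has failed.

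The cost is SAP wording and a few lines of code; no new data are needed. The downside for the sponsor is that the reported tipping value may look less favourable.
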